Definitions	
-Reference diagnosis: it will be done a posteriori by a panel of experts, including one radiologist, who will have access to all imaging studies (CXR, LUS, and LDCT), along with all clinical and biological data, including follow-up data up to one month after admission. They will give their probability of pneumonia, aspiration pneumonia, bacterial vs viral pneumonia or alternative diagnosis.
 
-Time to clinical stability: number of days from admission to the first time all of the following parameters are above/under the threshold value and maintained for a minimum of 24 hours: heart rate <100 beats/min, systolic blood pressure >90 mmHg, temperature <37.8°C (axillary or tympanic), respiratory rate <24 breath/min, oxygen saturation >90% while breathing room air, or need for more than 28% fraction of inspired oxygen to maintain adequate oxygen saturation, resolution of delirium if present at admission)

	
-Viral pneumonia: presence of an infiltrate on CT scan and a PCR positive for a virus
 
-Aspiration pneumonia: compatible radiological findings witnessed aspiration or risk factors for aspiration

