3.2 Primary and secondary endpoints

Primary outcome measure:

The primary outcome will be the difference in accuracy between LDCT and CXR, assessed at the end of the ED evaluation, using the expert panel as the reference standard, accuracy being computed as (true positive + true negative cases) / (true positive + true negative + false positive + false negative cases).-

Main secondary outcome measures:

Diagnostic outcomes:

- Difference in accuracy between LUS and CXR, assessed at the end of the ED evaluation, using the expert panel as the reference standard
- Sensitivity, specificity of CXR, LDCT and LUS
- Number of additional imaging studies and invasive procedures prescribed during the acute setting
- Prevalence of viral pneumonia
- Prevalence of unmasked imaging results (for an emergency finding)
- Prevalence of incidentalomas

Treatment outcomes:

- Number of antibiotic free days at day 30

Clinical outcomes:

- Time to clinical stability during the first 2 weeks (number of days from admission to the first time all of the following parameters are above/under the threshold value and maintained for a minimum of 24 hours: heart rate <100 beats/min, systolic blood pressure >90 mmHg, temperature <37.8°C (axillary or tympanic), respiratory rate <24 breath/min, oxygen saturation >90% while breathing room air, or need for more than 28% fraction of inspired oxygen to maintain adequate oxygen saturation, resolution of delirium if present at admission)
- Length of hospital stay (in the ED and in the acute setting)
- Proportion of patients with an unplanned transfer to the ICU
- Proportion of patients admitted to rehabilitation or LTCF days through 3 months
- All-cause mortality through 1 month and 3 months
- All-cause readmission to the acute care setting through 1 month and 3 months
- Quality of life at admission, discharge and 3 months (measured by EQ-5D-3L and a CAP score questionnaire)
 - Interagreement rate for the probability of pneumonia between physicians participating to the trial and a consensus of experts in chest imaging, for each method

- Association between biological markers (CRP and PCT) and the presence of an infiltrate

Cost outcomes:

Costs of care, physician, imaging, laboratory, treatment (including antibiotic therapy) and others per patient, health related quality of life until 3 months; unit of work consumption per hospital (number of minutes of care, physician, laboratory and imaging points)

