#### Diagnosis outcomes

- Unmasked imaging modalities in emergency
- Alternative diagnoses
- Diagnosis of aspiration pneumonia (yes/no)
- Type of pneumonia (viral/bacterial)
- Additional imaging studies ordered

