### 8.1.2.2 Diagnostic outcomes

The outcomes to be analysed may consist of either

- (1) the response provided by the **physician in charge**, or
- (2) the response from the **study expert investigator** following the first round of the

**Delphi survey.** At that stage, the expert only has access to REDCap data — i.e., the examination results — but not the imaging series or the full patient record.

- **Unmasked imaging modalities in emergency.** Urgent need to unblind the examination in case of immediately life-threatening findings (yes/no) was collected for each exam (CXR / LDCT / LUS). See [Box2](#).
- **Alternative/concomitant diagnoses** provided by (2) the **study expert** following the 1st round of the Delphi survey. Experts were asked about:
  - **alternative** diagnosis in case of a *low* probability of pneumonia
  - **concomitant** diagnosis in case of an *intermediate* or *higher* probability of pneumonia.the experts could choose among
  - Cardiac Failure
  - Exacerbation COPD/emphysema/asthma
  - Acute bronchitis
  - Pulmonary malignancy
  - Interstitial lung disease
  - Pneumothorax
  - Other
- **Probability of aspiration pneumonia** provided by (2) the **study expert**. Experts were asked to rate the probability as low/intermediate/high in case of a *low* probability of pneumonia
- **Type of pneumonia** according to (2) the **study expert** (viral or bacterial). Experts were asked to provide the type of pneumonia in case of a *low* probability of pneumonia.
- **Additional imaging studies ordered during the acute setting** by (1) the **physician in charge**  
The following additional imaging performed by the physician in charge were collected. For each type of imaging, its number was also collected
  - Chest X Ray
  - Pulmonary CT scanner
  - Lung ultrasound by radiologist
  - Echocardiography by a cardiologist
- **Other procedures prescribed during the acute setting** by (1) the **physician in charge**
  - Non-invasive ventilation
  - Pleural puncture (“*thoracentesis*”, indicated in the one month visit *instrument*)

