#### **Microbiological data**

Positive culture

Blood culture, n/N (%)

Urinary culture, n/N (%)

Sputum culture, n/N (%)

Positive urinary antigen

Legionella, n/N (%)

Pneumococcal, n/N (%)

PCR positive for *Mycoplasma pneumoniae*, n/N (%)

PCR positive for *Chlamydia pneumoniae*, n/N (%)

PCR positive for viruses, n/N (%)

PCR positive for SARS-CoV-2, n/N (%)

Endotracheal aspirate, n/N (%)

Bronchoalveolar lavage, n/N (%)

Pleural culture, n/N (%)

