#### 8.2.3.2 Diagnostic outcomes

Unless otherwise stated, diagnostic outcomes will be analysed solely for descriptive purposes, as count and percentages for qualitative variables, and mean and standard deviation for quantitative variables.

- ❖ **Non-invasive ventilation, pleural puncture, and additional imaging studies ordered** during the acute setting will be described as follow

Diagnostic outcomes	CXR (n=XXX)	LDCT (n=YYY)	LUS (n=ZZZ)
Patients with additional studies ordered, n (%)			
Yes (nb_imaging_ordered>0)			
No			
Number of additional studies ordered, mean (sd)			
Overall number (nb_imaging_ordered)			
Number of chest X Ray			
Number of Pulmonary CT scanner			
Number of Lung US			
Number of Echocardiography			
Patients with non-invasive ventilation, n (%)			
Patients with pleural puncture, n (%)			

The proportion of patients with additional studies ordered will be compared between arms using a linear probability model (binomial model with link Identity)

- ❖ The **following outcomes** will be described in **patients with a 'low' probability of pneumonia** according to the study expert:
  - Alternative diagnosis according to the study expert
- ❖ The **following outcomes** will be described in **patients with a 'intermediate' or 'high' probability of pneumonia** according to the study expert:
  - Probability of aspiration pneumonia according to the study expert
  - Type of pneumonia (viral & aspiration) according to the study expert

Diagnostic outcomes in patients with 'low' probability of pneumonia according to the study expert	CXR (n=XXX)	LDCT (n=YYY)	LUS (n=ZZZ)
Alternative diagnosis according to the study expert, n (%)			
Cardiac Failure			
Exacerbation COPD/emphysema/asthma			
Acute bronchitis			
Pulmonary malignancy			
Interstitial lung disease			
Pneumothorax			
Other			
Probability of aspiration pneumonia according to the study expert, n (%)			
Low			
Intermediate			
High			
Type of pneumonia according to the study expert, n (%)			
Viral			
Bacterial			

- ❖ **Concomitant diagnosis according to the study expert** will be described in **patients with an 'intermediate' or 'high' probability of pneumonia** according to the study expert:

Diagnostic outcomes in patients with 'intermediate' or 'high' probability of pneumonia according to study expert	CXR (n=XXX)	LDCT (n=YYY)	LUS (n=ZZZ)
Concomitant diagnosis according to the study expert, n (%)			
Cardiac Failure			

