Imaging suggestive of pneumonia, but a chronic lung condition or heart failure is also present; however, pneumonia probably explains most of the clinical findings

**Pneumonia possible** (34-66% of probability)

Imaging compatible with pneumonia, but another disease could as well explain the findings (acute heart failure with moderate inflammatory biomarkers; known diffuse lung disease with acute symptoms and worsening radiology, known lung cancer with acute symptoms and worsening radiology). However, most clinicians would probably choose to treat with antibiotics.

**Pneumonia unlikely** (10-33% probability)

Imaging compatible with pneumonia, but another disease may better explain the image (pulmonary embolism with lung infarction; large atelectasis with few findings of acute infection).

**Pneumonia excluded** (less than 10% of probability):

No infiltrate on all imaging studies

Faint infiltrate or imaging suggestive of an acute lung condition (heart failure, nodules / mass...), AND another disease is evident (abdominal or urinary sepsis; acute heart failure; cancer)

Response to antibiotic treatment should be considered with caution because of frequent concomitant treatment in that population (diuretics, bronchodilators, corticosteroids)

The five levels will then be reduced to three (1 and 2: high probability; 3: intermediate probability; 4-5: low probability), to concord with the protocol. The diagnostic threshold will separate 1-3 from 4-5.

If pneumonia is rated as excluded or unlikely, the experts will be asked to propose an alternative diagnosis for the symptoms of the patient: congestive heart failure, exacerbation of COPD, other

non-pneumonic respiratory infection (acute bronchitis), pulmonary malignancy, interstitial lung disease, pneumothorax, other

If pneumonia is rated as possible, probable or very likely, the experts will be asked two further questions:

- 'Do you think it is aspiration pneumonia (Y/N)
- "Do you think it is a viral pneumonia (i.e. without bacterial superinfection Y/N) if pneumonia is possible, probable or certain?

**5/ Validity and reproducibility** of the diagnosis: agreement between groups of experts will be assessed in a random sample of patients

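### The protocol's rule for viral pneumonia (CT infiltrate plus virus-positive PCR) and the SAP's expert item (viral only if no bacterial superinfection) classify mixed infections differently, and the SAP neither reports the protocol's version nor declares the change

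*SAP*

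**What the plan says.** **Protocol.** The Definitions block of the synopsis gives a rule: "Viral pneumonia: presence of an infiltrate on CT scan and a PCR positive for a virus". It makes no exception for bacterial co-infection. The same block says of the expert panel: "They will give their probability of pneumonia, aspiration pneumonia, bacterial vs viral pneumonia or alternative diagnosis". The protocol therefore holds a rule and, beside it, a panel judgement. Section 3.2 lists "Prevalence of viral pneumonia" among the secondary diagnostic outcomes, without a denominator.

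**SAP.** Section 3.3.2 lists the outcome as "Type of pneumonia (viral/bacterial", with only those two categories. Section 8.1.2.2 takes it from the study expert after the first Delphi round, when that expert has the REDCap data but not the images or the full record. Part 4 of the appendix on the expert panel method words the question as "Do you think it is a viral pneumonia (i.e. without bacterial superinfection Y/N) if pneumonia is possible, probable or certain". The table shell in section 8.2.3.2 has a viral row and a bacterial row and no others. Viral PCR appears in the Table 1 shell as "PCR positive for viruses, n/N", but no SAP outcome is built on it. Section 9 lists one dropped analysis, time to clinical stability, and says nothing about viral pneumonia.

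**The concern.** Two definitions are in play and they part company on an identifiable group. The protocol's rule asks whether a virus was found in a patient with an infiltrate. The SAP's question asks whether an expert believes a virus alone is responsible. A mixed infection satisfies the first and fails the second.

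The two-row shell adds a second difficulty. The appendix question is yes or no, while the table is viral or bacterial. Mixed infections and pneumonias with no pathogen found have no row of their own. The appendix itself allows a rating of very likely or confirmed when no pathogen was identified, so such patients are to be expected.

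What is at stake is whether a reader holding the protocol can interpret the published figure. They would take a viral percentage to mean infiltrate plus PCR, and a bacterial percentage to mean bacterial disease. Neither reading would be safe.

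**Working it through.** There is no figure in the plan to reproduce: neither document states a viral pneumonia prevalence, a PCR positivity rate or a superinfection rate. The check is first a comparison of definitions, then a range under stated assumptions.

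**Step 1. Classify the same patients under both definitions** (all taken to be rated possible or higher by the experts).

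| Patient | Protocol rule | SAP expert item |
|---|---|---|
| CT infiltrate, viral PCR positive, no superinfection judged | viral | viral |
| CT infiltrate, viral PCR positive, superinfection judged | viral | not viral |
| Viral PCR negative or not done, expert thinks viral | not viral, or cannot be classified | viral |
| No pathogen found, expert does not think viral | not viral | not viral; the only other row is the bacterial one |

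Rows two and three move in opposite directions.

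**Step 2. Size of the movement.** Let
- a = share of all patients meeting the protocol rule (assumed 15–35%);
- m = share of those judged superinfected (assumed 10–40%);
- v = share of all patients called viral by experts without meeting the rule (unknown);
- N = 495, the recruitment target in SAP section 3.5.

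On one common denominator, the protocol prevalence is a and the SAP prevalence is a(1 − m) + v. The change is v − a × m.

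| a | m | Protocol n | SAP n if v = 0 | Points lost if v = 0 | v that cancels the loss |
|---|---|---|---|---|---|
| 15% | 10% | 74 | 67 | 1.5 | 1.5% |
| 25% | 20% | 124 | 99 | 5.0 | 5.0% |
| 35% | 40% | 173 | 104 | 14.0 | 14.0% |

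**Step 3. Denominator.** The appendix asks the question only when pneumonia is rated possible or higher; the protocol states no denominator. Let π be the share of patients rated pneumonia-positive (assumed 40–60%), and suppose everyone meeting the rule is among them. With v = 0 the SAP percentage is a(1 − m)/π. At a = 25% and m = 20% this is 0.20/0.60 = 33% to 0.20/0.40 = 50%, against 25% of all patients under the protocol rule. It drops below a only if m > 1 − π. With π at most 60% that needs m above 40%, which is beyond the assumed range. The choice of denominator can therefore outweigh the change of definition.

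**Step 4. Can the protocol rule be applied?** Viral PCR was collected, but the n/N format implies that not everyone was tested. An LDCT infiltrate variable is not shown in the SAP: section 8.1.2.1 has imaging readers give a three-level probability of pneumonia, and Table 1 lists only image quality and reader experience for LDCT. Protocol sections 3.2 and 5.1 plan an analysis of biomarkers against infiltrates, which suggests that an infiltrate item was intended. Whether it exists has to be checked in the database.

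**A neighbouring inconsistency.** SAP section 8.1.2.2 says "Experts were asked to provide the type of pneumonia in case of a *low* probability of pneumonia", and the table heading in section 8.2.3.2 agrees. The text of section 8.2.3.2 instead puts "Type of pneumonia (viral & aspiration) according to the study expert" under intermediate or high probability, as the appendix does. That concerns who is classified rather than what counts as viral, but the denominator cannot be stated until it is settled.

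**The case against.** The best defence is that the protocol already planned expert typing. Its Definitions block has the panel separate bacterial from viral pneumonia, so the SAP did not invent an opinion-based outcome in place of an objective one. The appendix also states that it was first submitted in May 2025, before the earliest SAP version in the version history (June 2025). This stands, and it rules out reading the SAP as a late swap. It does not remove the mismatch: the same block says what viral pneumonia means, and nothing there lets the panel set aside the CT and PCR criteria or exclude mixed infection.

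Three stronger readings are tempting, and the documents do not support them.

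- *Reported prevalence will fall.* Mixed cases do leave the viral group, but the expert item requires neither PCR nor CT, so others can enter it, and the protocol fixes no denominator. The net direction is open.
- *Every no answer is counted as bacterial.* The shell makes this possible, but no text maps a no to that row and the CRF response options are not in the documents. The rows are also labelled as the expert's view, so they do not claim proven bacterial disease.
- *The antibiotic findings are affected.* The antibiotic-free-days analysis in SAP section 8.2.3.3 does not use pneumonia type.

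It is also fair to say that the outcome is minor. SAP section 8.2.3.2 treats diagnostic outcomes as descriptive unless stated otherwise, no between-arm comparison of type is planned, and viral prevalence is absent from the synopsis endpoint list and from the analyses in protocol section 5.1.

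**Conclusion.** The point holds in a limited form. The two documents define viral pneumonia differently, a patient with a CT infiltrate, a positive viral PCR and judged superinfection changes category between them, the two-row table has no place for mixed or undetermined cases, and section 9 does not declare the departure from the protocol's rule. These statements rest on the texts alone.

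The size does not. The 1.5 to 14 point movement depends on assumed rates of PCR-confirmed viral infiltrates and of superinfection, on a common denominator and on no offsetting expert calls; with other choices the percentage could stay level or rise. Since both definitions apply to the same patients, the difference is reclassification, and a standard error is not the scale on which to judge it. The primary comparison of diagnostic accuracy is unaffected. The change is still worth making, because the published figure would otherwise not match the protocol outcome it appears to answer.

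**What to change.** In SAP sections 8.1.2.2 and 8.2.3.2:

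1. Derive the protocol outcome (LDCT infiltrate, if recorded, plus virus-positive PCR) among PCR-tested patients. Report its prevalence with a stated denominator, the number untested and a 95% CI; the Clopper-Pearson method already in the SAP will do.
2. Report the expert item separately under its own label, for example *viral without bacterial superinfection: yes/no*, with the patients in whom it was asked stated.
3. Rename the bacterial row *not purely viral (bacterial, mixed or undetermined)*.
4. Declare in section 9 that the expert classification differs from the protocol's rule. If the LDCT infiltrate was not recorded, say so there and do not present the expert item as the protocol outcome.

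While editing, reconcile the low versus intermediate-or-high statements so that the denominator is unambiguous.

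The cost is SAP wording, one table shell and one derived variable. Section 1 of the SAP says it was finalised before analysis began, so on that footing the change can be made without sight of results.

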**Nota bene:**

This document was first submitted on Clinical Trial on May 2025.

It is re-submitted on January 2026 with no major modification except for the Official Title of the study, NCT number, and date of the document, added as required.
